Unilateral hearing loss (UHL) is a term used to describe a substantial hearing loss in one ear and normal hearing in the contralateral ear. Often patients with UHL have reduced speech perception in the affected ear, limiting the effectiveness of conventional amplification. Despite normal hearing in one ear, these patients experience reduced speech perception in noise (Welsh et al, 2004; Rothpletz, Wightman & Kistler, 2012), variable abilities on localization tasks (Slattery & Middlebrooks, 1994), increased reports of hearing handicap (Iwasaki et al, 2013), and reduced quality of life (Wie, Pripp & Tveten, 2010).

In the United States, the prevalence of UHL in children ranges from 0.03% to 3%, depending on the age of the child (Porter & Bess, 2011). Studies have indicated that of the children screened for hearing loss at birth, 0.03% have unilateral hearing loss, and of the children screened at school-age, the prevalence rises to 3% (Bess, et al, 1998). Although the premise that UHL creates educational, social and behavioral challenges for children has been acknowledged for several decades (Bess, 1986; Bess, et al, 1986; Lieu, 2004; Ruscetta et al, 2005; Tharpe, 2008; Borton, et al, 2010), our ability to treat and provide habilitation for such children has been limited to strategic interventions, such as preferential seating, or less effective technologies, such as hearing aids or bone-conduction devices. For children with moderate to profound hearing loss in one ear, a traditional hearing aid in the poorer ear typically provides inadequate amplification and poor sound quality due to the inability to provide sufficient audibility in the speech spectrum. CROS hearing aids and bone-conduction devices route the signal from the affected side to the better hearing ear. A CROS hearing aid uses a microphone/transmitter on the affected ear to send the acoustic signal to the receiver on the better hearing ear. Studies assessing the efficacy of CROS hearing aids in children have been performed. They indicate benefit for quality of life and speech recognition in quiet; however, these results were for children with thresholds in the mild to moderately-severe range (Kenworthy, et al, 1990; Updike, 1994; Briggs, et al, 2011). Bone-conduction devices use vibratory stimulation to transmit the signal to the cochlea on the side with better hearing. In a similar fashion to CROS aids, bone conduction aids route the signal to the better hearing ear, stimulating only one auditory pathway. Though listeners receive signals from both sides, they are unable to use binaural cues. This inability to stimulate both auditory pathway results in variable speech perception in noise (Kunst et al, 2007) and poor localization (Bosman et al, 2003; Hol et al, 2010). It is hypothesized that a cochlear implant, which would stimulate the auditory pathway on the affected side, may benefit this population by improving speech perception in the affected ear and offering binaural cues for improved localization and speech perception in noise.

A cochlear implant is a two-part system, including the internal receiver/electrode array and external speech processor. The internal receiver/electrode array is surgically implanted into the cochlea. The external speech processor detects sounds and codes and transmits this signal to the internal portion. The acoustic signal is presented through the implanted device within the cochlea via electrical pulses. Sound is then perceived and interpreted by the brain. Cochlear implantation performed for children with bilateral, severe to profound deafness has significant impacts on several aspects of child development. First, children who are deaf and are implanted early can acquire spoken language in a manner that follows the developmental trajectory experienced by children with normal hearing (Nicholas & Geers, 2007). These children have both better access to, and use of sound due to improved speech perception and better expressive and receptive language (Niparko, et al, 2010). Second, access to sound also stimulates social and emotional growth and development (Nicholas & Geers, 2003). Third, quality of life is perceived by parents and teachers as being improved for children with cochlear implants relative to their non-implanted peers (Stacy, et al, 2006). There is evidence that cochlear

implantation can stave off neurologically driven sensory deficits that impact neuro-cognitive development. Finally, children with unilateral hearing loss appear to require greater auditory effort to understand speech. In a classroom setting, this can result in greater fatigue in multiple domains including cognitive fatigue, thus leading to negative impacts on learning (Hornsby et al 2013). As audition is integrated into brain functions such as sequencing, sensory-motor control, and executive function, the lack of hearing from an early age may have cascading negative effects on higher level brain functions (Conway, Pisoni, Kronenberger, 2009; Sharma, Dorman, Spahr, 2002).

In Europe, cochlear implantation has become an accepted treatment for patients with UHL. The majority of literature regarding patients with UHL and cochlear implantation involves adults. It has been reported as a viable treatment option in cases of UHL, including sudden sensorineural hearing loss (Firszt et al, 2012), and severe tinnitus (Vermiere & Van de Heyning, 2009; Van de Heyning et al, 2008). Further, cochlear implantation has been shown to offer superior speech perception in noise, sound localization abilities, and subjective perception of hearing quality compared to CROS hearing aids and bone-conduction devices (Arndt et al, 2011).

The practice of providing cochlear implants to children who have significant hearing loss in one ear is of great interest and is occurring with greater frequency as reported in case studies and small set clinical reports (Gantz, et al. 2000, Cadieux et al., 2013; Hassepass, et al., 2013; Plontke et al., 2013; Tzifa and Hanvey, 2013; Távora-Vieirea and Rajan, 2015; Arndt, et al, 2015). Children with severe to profound UHL may have greater potential to benefit from cochlear implantation than adults with UHL from a developmental point of view due to their neural plasticity. They may be more amenable to gaining binaural listening skills after cochlear implantation.

The primary goal of this project is to determine whether children with UHL experience an improvement in speech perception, hearing in noise, localization, and quality of life with a cochlear implant as compared to an unaided listening condition.

2) Objective

The primary purpose of this feasibility study is to demonstrate the effectiveness of cochlear implantation in children with moderate to profound UHL. Postoperative results will be evaluated with:

- i) speech perception measures,
- ii) localization tasks,
- iii) hearing in noise tasks,
- iv) subjective reports.

3) Definitions

Adjusted Constant Error: the rms deviation of the mean responses from the diagonal, computed after compensating for bias. This procedure reduces the bias

when evaluating the relationship between the average response on the azimuth and signal source on the azimuth.

Bone-Conduction Device: A device on the poorer hearing ear that picks up the acoustic signal on the effected side and transmits to the better hearing ear via vibrations through the skull. This is accomplished by either securing the oscillator to the head with a headband or via an implanted titanium abutment in the skull bone.

CNC words: A standardized word list comprised of 50 words with consonant-vowel-consonant construction ie, Consonant-Nucleus-Consonant (CNC) words (Peterson & Lehiste, 1962). The CNC test assesses perception of monosyllabic words. The test includes 10 lists of 50 words each. Each word is preceded by a carrier word “ready.”

Cochlear Implant (CI): A two-part system, including the internal electrode array and external speech processor that stimulates the auditory pathway on the effected side. The internal electrode array is surgically implanted into the affected cochlea. The external speech processor receives sounds and transmits this signal to the internal portion. The electrode array presents the acoustic signal via electrical pulses within the cochlear space, which is interpreted by the brain as sound.

Constant Error: the rms deviation of the average responses from the source positions

Contralateral Routing of Signal (CROS) Hearing Aids: A two-part system consisting of a transmitter microphone on the deafened ear and a receiver on the normal hearing ear. The transmitter sends the signal from the deafened ear to the normal hearing ear. The auditory pathway on the normal hearing ear receives the sound.

Desired Sensation Level (DSL): The Desired Sensation Level (DSL) Method was originally developed to provide audiologists with a systematic, science-based approach to pediatric hearing instrument fitting that ensures audibility of amplified speech by accounting for factors that are uniquely associated with the provision of amplification to infants and young children who have hearing loss (Seewald, Ross and Spiro, 1985; Ross and Seewald, 1988; Seewald and Ross, 1988).

Pure Tone Average (PTA): The average threshold (dB HL) from 500, 1000, and 2000 Hz

Random Error: the standard deviation of responses at each signal source position, averaged across all potential signal sources

Root-Mean-Square (rms) Error: The difference between the location on the azimuth of the sound source and the participant’s response on each trial for the localization task

4) Investigational Device

Participants will be implanted with the commercially available MED-EL Synchrony cochlear implant with the FLEX28 or FLEX24 electrode array (MED-EL Corporation, Innsbruck, Austria). The devices consist of a stimulator, a coil with a magnet within its center, a reference electrode, an EAP reference electrode and an active electrode permanently attached to the stimulator.

The FLEX28 Electrode Array is 28 mm long. The contacts for the 12 channels are arranged as 5 single contacts at the apical array end and 7 contact pairs at the base, with a 2.1 mm spacing between each channel. The marker ring is located 28 mm from the electrode tip and indicates the deepest insertion.

The FLEX24 Electrode Array also features 12 electrode contacts, with five at the apical end and 7 at the base. This array is shorter than the FLEX28. The FLEX24 is 24 mm long and contacts are spaced 1.9 mm apart. The marker ring is 24 mm from the tip to indicate deepest insertion. This array is designed for a more shallow insertion depth.

Both arrays feature FLEX tip technology. The specially designed electrode tip offer increased mechanical flexibility for reduced insertion force. Near the marker ring, the electrode leads feature an additional marker on the same side of the array as the single apical contacts. The marker allows the surgeon to ensure appropriate alignment of the single contacts toward the modiolus.

The MED-EL audio processor is an external component of the MAESTRO Cochlear Implant System and is indicated for use on patients who have been implanted with a MED-EL cochlear implant. The audio processor analyzes the sound signal from the microphone according to the selected speech coding strategy and transforms it into a coded electrical signal that is sent to the externally worn coil. This coded signal contains information about how to stimulate the individual electrodes, so changes in pitch and loudness can be perceived. The coil, which is magnetically held in place over the implant, sends the coded signal across the skin to the implant package via an inductive link.

Programming of the device is completed using the MAX Programming Interface and MAESTRO System Software. The MAESTRO software is used for different intraoperative and postoperative purposes for the MED-EL Cochlear Implant System. It contains the implant Telemetry, Fitting and Configuration of all available audio processors, ART (Auditory nerve Response Telemetry), ESRT (Electrically Evoked Stapedius Reflex Threshold), EABR (Evoked Auditory Brainstem Response) and Audiogram functions. The MAESTRO software is an external component of the MED-EL Cochlear Implant System and is intended to be used in a clinical or office environment by persons adequately skilled and trained to perform all intended tasks and with patients who received one of the intended MED-EL Cochlear implants.

For the pediatric population, the MED-EL Synchrony cochlear implant is currently indicated for children 12 months to 17 years and 11 months of age, who have bilateral sensorineural hearing impairment and obtain limited benefit from appropriately fitted binaural hearing aids. In this study, the use of this system is considered investigational because it will be used for children who have unilateral moderate to profound sensorineural hearing loss rather than bilateral profound sensorineural hearing loss.

5) Study Duration

- a) Enrollment Period
4 years

- b) Study Timeline

Each participant's involvement will last approximately 2.5 years, including: candidacy evaluation, preoperative evaluation, surgical procedure, initial activation of the external speech processor, therapy schedule, and post-initial activation evaluations (3, 6, 9, 12, 18 and 24-months post-initial activation).

- c) Study Endpoint

The study endpoint for each participant is the 24-months post-initial activation interval.

6) Methods

- a) All procedures will be conducted by UNC investigators, including board-certified otologists, audiologists, and speech-language pathologists. Fully informed consent will be obtained from all participants and/or their parents.
- b) Participants must meet the following inclusion criteria and not exhibit any of the exclusion criteria.
 - i) Inclusion Criteria
 - (1) Unilateral moderate-to-profound sensorineural hearing loss.
 - (a) Unaided residual hearing thresholds that yield a PTA at frequencies 500Hz, 1K Hz and 2K Hz of ≥ 70 dB HL in the ear to be implanted. It is possible that subjects may have hearing at other frequencies not included in this average.
 - (b) Hearing thresholds in the contralateral ear of ≤ 25 dB HL
 - (2) Between 3 years, 6 mos and 6 years, 6 mos of age at implantation.
 - (3) Anatomically normal cochlear nerve
 - (4) Cochlear anatomy that is amenable to cochlear implantation as evaluated by imaging (modality at the physician's discretion) including:
 - (a) Normal cochlear anatomy or

- (b) Incomplete Partition Type II (IP2) with or without Enlarged Vestibular Aqueduct (EVA) or
- (c) EVA with normal partitioning
- (5) No evidence of progressive hearing loss.
- (6) Willing to undergo 4 week hearing aid trial as warranted based on achieving desired audibility when fitted via real ear DSL method. See Reference Appendix B.
- (7) Aided word recognition in the ear to be implanted of 30% or less as measured with CNC words (50-word list)
 - (a) When listening with an appropriately fit hearing aid and masking applied to the contralateral ear (Turner, 2004).
 - (b) Aided testing will be conducted in a sound-proof booth with the participant seated 1 meter from the sound source, facing 0° azimuth. Recorded materials will be presented at 60 dB SPL.
 - (c) The hearing aid output will be measured using DSL targets.
- (8) Realistic parental expectations: *a verbal acknowledgement of the potential benefits and risks, and postoperative variation in performance. For instance, cochlear implantation will not restore normal hearing.*
- (9) Willing to obtain recommended meningitis vaccinations per CDC recommendations.
- (9) Development and cognition within the normal range as measured by the Leiter-R test of nonverbal intelligence and cognitive abilities.
- (10) Parental commitment to study parameters including being able and willing to participate in evaluation schedule, involvement in prescribed therapy, and travel to investigational site and study-related activities.

ii) Exclusion Criteria

- (1) English is not primary language of the home
 - (a) Speech perception materials are presented in English
 - (b) Parental questionnaires are administered in English
- (2) Conductive hearing loss in either ear
- (3) Compromised auditory nerve
- (4) Ossification of the cochlea
- (5) Inability to participate in follow-up procedures (i.e., unwillingness, geographic location)
- (6) History of condition that contraindicates middle or inner ear surgery or anesthesia (i.e. otitis media refractory to treatment)
- (7) Case of sudden sensorineural hearing loss that has not been first evaluated by a physician

iii) Enrollment

- (2) This study seeks to enroll twenty (20) participants.

c) Timeline

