
- (3) Test materials to include:
 - (a) 3 subtests of Early Speech Perception Test (ESP), if > 70% then,
 - (b) CNC words
- iv) Speech Perception in Noise in binaural condition (6, 12, and 24 months post-initial activation)
 - (1) Speech processor on
 - (a) Listening conditions, noise orientation
 - (i) Speech and noise at 0° azimuth.
 - (ii) Speech 0° azimuth and noise to implanted side
 - (iii) Speech 0° azimuth and noise to contralateral ear
 - (b) Speech perception materials
 - (i) BKB-SIN
 - (2) Speech processor off
 - (a) Listening conditions, noise orientation
 - (i) Speech and noise at 0° azimuth.
 - (ii) Speech 0° azimuth and noise to implanted side
 - (iii) Speech 0° azimuth and noise to contralateral ear
 - (b) Speech perception materials
 - (i) BKB-SIN
- v) Sound Field Localization Measures (3, 9, 18, and 24 months post-initial activation)
 - (1) Postoperative aided sound field assessment will be measured in the free field with the Sonnet speech processor turned on and with the processor turned off.
 - (2) Testing will be completed in a double-walled soundproof booth. Eleven loudspeakers are arrayed in a 180-degree arc, with speakers evenly spaced at 18-degree intervals. Speakers are mounted at ear level, all spaced approximately 1-meter from the listener.
 - (3) The stimulus is a 200-ms speech-shaped noise, presented at 70-dB SPL. The speaker used to present the stimulus is randomly selected from the 11 alternatives on each trial, with the caveat that each speaker is used 3 times during a block of 33 trials. At least one block of 33 trials will be obtained in each condition (with and without the processor turned on).
 - (4) The listener faces the middle speaker prior to and during stimulus presentation. The task is to identify the source of the noise. Feedback is provided during instruction and training trials, but not during data collection.
 - (5) Listening Conditions
 - (a) Cochlear implant speech processor off at the 3, 9, 18 and 24 month intervals
 - (b) Cochlear implant speech processor on at the 3, 9, 18 and 24 month intervals

- (6) Performance is analyzed by computing the normalized RMS error, a metric that characterizes a listener's ability to discriminate between sound source locations.
- (7) These procedures have been used successfully to test children as young as 4 years of age.

vi) Parent questionnaires

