- b) A single-subject design will be utilized, where each participant serves as his or her own control, for analysis of objective and subjective results. A single-subject design was chosen in order to accommodate the heterogeneity that is well known to characterize auditory prosthesis research. Repeated-measures ANOVA will be calculated with a p-value of ≤ 0.05 for statistical significance. Statistical analysis will be conducted with SPSS software.
 - i) Comparison of aided speech perception performance to the baseline condition (either unaided or aided with hearing aid, depending on the participants residual hearing) and in the post-initial activation intervals to evaluate trends over time
 - ii) Comparison of localization abilities to the baseline condition (either unaided or aided with hearing aid, depending on the participant's residual hearing) and in the post-initial activation intervals to evaluate trends over time
 - iii) Compute the overall rms error, random error, constant error, and adjusted constant error, as described by Grantham et al (2007)
 - iv) Comparison of subjective report scores in the post-initial activation intervals. Group means compared with Bonferroni's adjusted t tests or repeated-measure ANOVAs. Pearson's correlations will be used to analyze relationships between variables.
 - v) Subjective report scores will be compared to norms for this test. Group means compared with Bonferroni's adjusted t tests or repeated-measure ANOVAs. Pearson's correlations will be used to analyze relationships between variables.
- c) The incidence of interference between ears will be assessed at the 6,12 and 24 month post initial stimulation visit by comparing the speech perception performance in the 0° azimuth conditions for the contralateral ear only versus cochlear implant + contralateral ear conditions for each participant, as well as the individual's subjective report.

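### Constant and adjusted constant localization error absorb response scatter, because they can rest on three responses per speaker, and block counts need not match between processor on and off

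*Combined protocol and SAP*

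**What the plan says.** All references are to the combined protocol and SAP.

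- **Definitions (section 3).** Random error is "the standard deviation of responses at each signal source position, averaged across all potential signal sources". Constant error is "the rms deviation of the average responses from the source positions". Adjusted constant error is the same kind of quantity after an overall response bias is removed. No divisor for the standard deviation is given, and none of the three is corrected for the number of responses behind it.
- **Task (section 6.d.v(2) and (3)).** "Eleven loudspeakers are arrayed in a 180-degree arc, with speakers evenly spaced at 18-degree intervals", and "each speaker is used 3 times during a block of 33 trials". On quantity: "At least one block of 33 trials will be obtained in each condition". There is no upper limit, no rule for adding a block, and no requirement that on and off have the same number.
- **Conditions (section 6.d.v(1) and (5)).** Children are tested "with the Sonnet speech processor turned on and with the processor turned off" at 3, 9, 18 and 24 months.
- **Measures.** Section 6.d.v(6) says "Performance is analyzed by computing the normalized RMS error", with the normalization undefined. Section 8.b.iii says "Compute the overall rms error, random error, constant error, and adjusted constant error", citing a published 2007 method. None of the four is designated as the main one.

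**The concern.** Splitting localization error into a random and a systematic part is useful only if each part responds to its own cause. A mean of three responses still carries much of the scatter of single responses, and constant error treats that residue as systematic displacement. If the implant makes a child more consistent without shifting where the child points on average, constant error falls anyway. The report would then credit the device with less systematic error when only consistency had improved.

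The open-ended block count adds a second route. The distortion shrinks as responses accumulate, so a condition that regularly receives more blocks shows lower constant error and higher random error with no true difference. Localization is one component of the primary effectiveness endpoint (section 9.b), and the on-off contrast is the one in the proposed claims (section 7.a.i).

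**Working it through.** **Inputs from the document.** 11 speakers, 18 degrees apart, 3 presentations each per block; 20 participants with about 20% dropout (section 8), hence about 16 completers; significance at 0.05 (section 8.b), taken as two-sided. Reproduced: 11 × 3 = 33 trials, and 10 gaps × 18 = 180 degrees, both as stated.

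**Assumed.** Response scatter s per speaker. The document gives no value, so 10 to 40 degrees is shown.

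**Constant error.** Let c be true constant error and n the responses per speaker. Each speaker mean has sampling variance s²/n, so the expected square of constant error is c² + s²/n. With one block, n = 3.

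- c = 20, s = 30: √(400 + 900/3) = √700 = 26.5
- c = 20, s = 15: √(400 + 225/3) = √475 = 21.8
- Gap with no change in c: 4.7 degrees
- c = 0: s/√3 = 5.8, 11.5, 17.3 and 23.1 degrees at s = 10, 20, 30 and 40

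If the bias removed is the mean signed error over the 11 speakers, adjusted constant error carries 10/11 of the same excess.

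**Check with responses limited to the 11 speakers.** Bounding the arc makes true constant error depend somewhat on scatter, so the long-run value is subtracted. Scatter falls from 40 to 20, three responses per speaker:

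- Responses compressed by half: observed 36.6 to 30.7 (fall 5.9), true 29.8 to 28.5 (fall 1.3). Spurious part 4.6.
- Responses centred on the source: observed 20.5 to 11.1 (fall 9.4), true 7.9 to 3.4 (fall 4.5). Spurious part 4.9.

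In a simulation with one block per condition and 16 children, scatter falling from 30 to 15 made constant error differ significantly in 61 to 99% of trials, depending on the assumed response pattern.

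**Random error.** The mean of per-speaker SDs underestimates s by the factor 0.886 at n = 3 and 0.952 at n = 6 (divisor n−1), or 0.724 and 0.869 (divisor n).

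**Overall rms error.** Taken as the root mean square over trials, its expected square is c² + s² whatever n is.

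**Unequal blocks, no true difference.** At c = 20 and s = 30, one block gives √(400 + 900/3) = 26.5 and two give √(400 + 900/6) = 23.5, a gap of 3.0 degrees. Percentage of simulated trials with p ≤ 0.05 (16 and 20 children; responses centred or compressed by half; mean scatter 30, between-child SD 6):

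| Blocks in the two conditions | Constant | Adjusted constant | Random (n−1) | Random (n) | Overall rms |
|---|---|---|---|---|---|
| 1 and 1 | 4–5 | 4–5 | 5–6 | 5–6 | 5 |
| 1 and 2, every child | 26–97 | 22–96 | 32–44 | 96–99 | 4–6 |
| 1 and 2 in a quarter of children, same direction | 6–11 | 6–11 | 6–7 | 11–16 | 4–6 |
| Counts vary at random | 5–6 | 5–6 | 5–6 | 5 | 4–6 |

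**The case against.** The strongest reply is that the measures most likely to be tested are sound. Section 6.d.v(6) names a form of rms error, section 8.b.iii lists overall rms error first and says only that the four are to be computed, and overall rms error does not move in any scheme above. This stands, and it confines the point to the decomposition. The normalized version is probably unaffected too, but its normalization is undefined.

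Second, a reader might infer that extra blocks will produce false on-off differences. The document does not support that. It sets a minimum per condition and nowhere says that the counts will differ. The high rates need every child to be unbalanced in the same direction. With a quarter of children affected they are 6 to 16%, and with random imbalance about 5%. Three responses is likewise the minimum, not a fixed number.

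Third, the downward bias in random error is harmless to an on-off test when blocks are equal, because it multiplies both conditions alike. Agreed; only the size of the reported difference shrinks.

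Fourth, a fall in scatter is a real localization gain, so only the label is wrong. That is fair, but the label is the reason for reporting the split.

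Fifth, the formulas follow a published method that cannot be seen here, and section 9.b states its contrast against the preoperative unaided condition, not against processor off. Both are reasons for restraint. Neither removes the s²/n term, which enters any comparison in which scatter differs.

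**Conclusion.** The point holds for the random/constant split. As section 3 defines them, constant and adjusted constant error have squares inflated by about s²/3 at the minimum of one block. Equal blocks do not remove this, because the inflation follows scatter, which can differ between conditions. The term is algebra. The degrees depend on assumed scatter: the example gives a spurious 4.7 degrees, and the bounded checks give 4.6 and 4.9.

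The block-count problem is conditional. It can produce false differences in random, constant and adjusted constant error if counts differ systematically by condition, which section 6.d.v(3) permits but does not prescribe.

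A reader might conclude that the localization endpoint as a whole is compromised. It is not: overall rms error kept a false-positive rate of about 4 to 6% in every scheme. For a feasibility study this is a correction that should be made to the analysis wording, not a flaw in the design.

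**What to change.** 1. **Section 6.d.v(3).** State that the same number of blocks is analysed in both conditions at each visit, using the first block or blocks of each if the numbers differ.
2. **Sections 6.d.v(6) and 8.b.iii.** Reconcile the metric names. Name overall rms error as the single localization measure tested, and make random, constant and adjusted constant error descriptive.
3. **Sections 3 and 8.b.iii.** Compute random error as the square root of the mean within-speaker variance, divisor n−1. For constant error, subtract s²/n from each speaker's squared mean deviation, average over speakers, and only then floor at zero and take the root. Apply the analogous correction to adjusted constant error (10/11 of the mean s²/n if the bias removed is the mean signed error).

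The order in item 3 matters. Flooring speaker by speaker left 9 to 95% rejection in the scatter-only simulation and up to 40% with one block against two. Flooring after averaging brought this to about 4 to 10%.

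The cost is wording and a few lines of code, with no added testing of children. The small downside is a departure from the published formulas, so report those alongside for comparability.
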